Using Gum Arabic for Cancer Patients to Protect From Oral Mucositis Caused by Chemotherapy: An Experimental Study

NCT ID not yet assigned

15/11/2017

Study protocol

Background

Investigate agents which can be used to prevent or treat chemotherapy-induced oral mucositis is a primary concern for clinicians and researchers. The synthesis pharmacological drugs are costly and associated with much side effects resulting in patient non-compliance. So, there is a need to find alternative therapies especially from natural sources as these are cost effective and have no or minimal side effects. In this regard, Gum Arabic is very convenient since this polymer is readily available on nature and does not require any further complex method of purification. Also it is a safe material for biological applications.

Objective of study

The purpose of this research was to investigate the effect of Gum Arabic to prevent chemotherapy-induced oral mucositis in cancer patients.

Inclusion criteria

Patients whom well diagnosed with cancer in any stage were eligible for enrolment if chemotherapy is a part of the treatment plan.

Exclusion criteria

Patients will be excluded if recently received chemotherapy or radiotherapy, presence of oral mucositis or periodontitis, or there is evidence of any systemic diseases.

Dose, preparation and administration of gum arabic

The daily dose of Gum Arabic will be divided in 30 grams sachet, the content of sachet will dissolve once in 100 ml purified water to form solution, and consuming

in six divided doses. Patient will provide by measuring cap to using 20-ml every two hours as mouthwash for a minute then swallow.

The total number of sachets are 42 for a period of six weeks; each patient will give 21 sachet of Gum Arabic at the first day of chemotherapy treatment to be used during the next three weeks of the treatment period, then the remain quantity (21 sachets) will provide for the next three weeks.

Modification on the preparation and administration

Because frequent use during the day (six times; each 2 hours) and high viscosity of gum arabic solution, which lead to withdrawn some patients after were enrolled in this study. Researcher was tried to solve this problem at two sides; firstly, by increasing the quantity of purified water as solvent for Gum Arabic to 250 milliliters instead of 100 milliliters to reduce viscosity of solution. On the other hand, patient was informed to use this quantity of solution twice daily; half at 9 morning and the remaining half at 9 evening to decrease frequent uses.

Oral mucositis assessment:

Based on a combination of subjective, objective and functional outcomes, using World Health Organization Oral Toxicity Scale (WHO Score): subjective – soreness as described by the patient, objective – presence of erythema and ulcerations, and functional – ability to eat solids, liquids or nothing by mouth

Assessment gum Arabic effect

For each participant data of oral mucositis will be start after getting ethical committee permission & permission from Radiation and Isotopes Center of Khartoum (RICK) authority. Informed consent also will be taken from study participants.

Data will gather via data collection sheet which composed of two sections; that will fill through six weeks of patient follow up. The first part for assessment patient regarding oral mucositis after chemotherapy by weekly telephone call for patient based on ready-scheduled appointments. The second part contain a basic information and characteristics of patient, which will record by researcher during the first day at first cycle of chemotherapy. In addition, there is meeting with patients by researcher in chemotherapy rooms when the participant return to the next cycle of chemotherapy either weekly, bi-weekly or every three weeks, according to treatment regimen.

When the researcher is contacted with the patient either by telephone call or when meeting participant in the hospital during the next chemotherapy cycle; there will be specific questions directed by the researcher to be answered by the patient regarding oral mucositis. Those questions will be summarized as follow: 1. Does the oral mucositis was occurred during this week? 2. If Yes. Is there was soreness, erythema, ulcers in mouth of participant? 3. The day that oral mucositis was started and eliminated? 4. If the patient belong to study group; Is Gum Arabic still used regularly? Six weeks for each participant from starting therapy.

Cessation of trial therapy

No stop for recruiting the participants to study group until the planned number was completed, but there was a period of three weeks the new recruitment was suspended to separate study group from control group in try to reduce the bias (reduce the confounding) between the two groups and give a chance to follow up the study group patients. By August 2016 we stopped participants recruitment and follow up; since the sample size proposed and follow up planned was completed.

Statistical analysis

The collected data were arranged, coded, tabulated, and introduced to a personal computer using Statistical Package for Social Science (IBM SPSS Statistics 20.lnk). P. values equal or less than 0.05 was considered significant. The data of 332 patients who completed this study were documented and reviewed to give a qualitative analysis of the frequencies. The descriptions were based on the data that documented from personal file of patient in designed sheet prepared by the researcher. Data were presented and suitable analysis was done according to the type of data obtained for each parameter. All numeric variables were expressed at 95% confidence intervals. Student t-test was used to assess the statistical significance of the difference between means of the two groups.

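### The outcome is named as a WHO score, but erythema and ulceration come only from patients' answers and eating is not among the listed questions; the data described do not support a WHO grade, and reporting error could bias the comparison either way

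*Combined protocol and SAP*

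**What the plan says.** The section headed Oral mucositis assessment names the WHO Oral Toxicity Scale and gives it three parts. Soreness is explicitly the patient's own description. The other two are "objective – presence of erythema and ulcerations" and "functional – ability to eat solids, liquids or nothing by mouth".

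The section headed Assessment gum Arabic effect says how the data are obtained:

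- The first part of the data sheet is for "assessment patient regarding oral mucositis after chemotherapy by weekly telephone call".
- In addition, "there is meeting with patients by researcher in chemotherapy rooms when the participant return to the next cycle of chemotherapy", at weekly, two-weekly or three-weekly intervals depending on regimen.
- At each contact, "either by telephone call or when meeting participant in the hospital during the next chemotherapy cycle", the procedure is the same: "there will be specific questions directed by the researcher to be answered by the patient regarding oral mucositis".

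Four questions follow, introduced as a summary: whether mucositis occurred that week; if so, "Is there was soreness, erythema, ulcers in mouth of participant"; the days on which it started and ended; and, for the study group only, whether gum arabic is still being used regularly.

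The Statistical analysis section does not mention the WHO score. It gives 332 completers without a split by group, a significance level of 0.05, and one named test, a Student t-test on group means. No event rates, power, or accuracy of patient report are given.

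**The concern.** The plan draws its own line between what the patient describes and what is objectively present, and the procedure then removes it. Soreness, erythema and ulceration share one question, put to the patient only after the patient has reported mucositis. The functional part has no listed question at all.

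Two things are at stake. The first is what the trial may claim: a WHO grade implies an objective and a functional assessment that the plan does not describe. The second is bias. An outcome known only through self-report carries reporting error, and here nothing in the design keeps that error equal between groups. The fourth question shows that the researcher knows who is taking gum arabic, and no blinding or placebo is described.

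**Working it through.** **Step 1. Named scale against described procedure.**

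| Part of the named scale | Described source |
|---|---|
| Soreness | Patient's answer (question 2) |
| Erythema, ulceration | Patient's answer (same question 2); no inspection described |
| Ability to eat | No listed question |
| Combination into a grade | No step described |

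The listed questions yield occurrence, a combined symptom-and-sign answer, and start and end days. They do not yield a grade.

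**Step 2. Direction and size of reporting error.** The plan has no figure to reproduce. All of the following are assumptions: true rates of 40% (control) and 25% (gum arabic), sensitivity (Se), specificity (Sp), 166 per group (332 / 2), and a two-sided 0.05 test of two proportions. Occurrence yes/no is used because question 1 asks for it.

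Observed rate = p × Se + (1 − p) × (1 − Sp).

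*Equal error, Se 0.80, Sp 0.90:*
- Control: 0.40 × 0.80 + 0.60 × 0.10 = 0.380
- Gum arabic: 0.25 × 0.80 + 0.75 × 0.10 = 0.275
- Difference: 10.5 points instead of 15. The retained fraction is Se + Sp − 1 = 0.70.

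Power = Φ[(d − 1.96 × SE₀) / SE₁], where d is the difference, SE₀ its standard error with pooled variance and SE₁ that with unpooled variance.
- True rates: d = 0.15, SE₀ = 0.0514, SE₁ = 0.0507, power 83%.
- Observed rates: d = 0.105, SE₀ = 0.0515, SE₁ = 0.0512, power 53%.
- Range: Se/Sp 0.90/0.95 keeps 85% of the difference (power 70%); 0.70/0.85 keeps 55% (power 36%).
- Splits of 111/221 or 221/111 lower the 83% and 53% by about 3 to 6 points.

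Even equal error need not shrink every measure. With Se 0.70 and Sp 1.0 the rates are 28.0% and 17.5%. The difference falls to 10.5 points, but the risk ratio stays at 0.175 / 0.280 = 0.625, the same as 0.25 / 0.40.

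*Error favouring gum arabic (control Se/Sp 0.85/0.85, gum arabic 0.70/0.95):*
- Control: 0.40 × 0.85 + 0.60 × 0.15 = 0.430
- Gum arabic: 0.25 × 0.70 + 0.75 × 0.05 = 0.2125
- Difference: 21.75 points, enlarged from 15.
- With no true effect (40% in both): control 0.430; gum arabic 0.40 × 0.70 + 0.60 × 0.05 = 0.310. The spurious difference is 12 points, significant about 62% of the time.

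*The reverse pattern:*
- Control: 0.40 × 0.70 + 0.60 × 0.05 = 0.310
- Gum arabic: 0.25 × 0.85 + 0.75 × 0.15 = 0.325
- The true 15-point benefit disappears.

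At true rates of 60% and 45%, equal error (0.80/0.90) again gives 10.5 points, and error favouring gum arabic gives 22.8.

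**Step 3. What was still possible.** The document is dated 15/11/2017, and its section on cessation says recruitment and follow-up stopped by August 2016. Six weeks would have allowed on-schedule return meetings on days 8, 15, 22, 29 and 36 (weekly regimen), 15 and 29 (two-weekly) or 22 (three-weekly). Those meetings are past.

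**The case against.** The best defence is that the text is brief, not that the procedure is sound. The questions are expressly a summary, the researcher did meet patients face to face, and the Statistical analysis section mentions data from the patient's personal file. An inspection or an eating question could have existed unrecorded in this document. That stands against one tempting inference, that the signs were never observed. The supportable statement is that no inspection is described. It does not rescue the label, because following the plan as written still gives self-report.

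A reader might also infer that misclassification shrinks any true effect, so that a positive result would be conservative. The documents do not support this. It needs error equal in both groups, and the group is known to the questioner.

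A third inference, that results have already been misreported as WHO scores, fails because the documents contain no results.

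The arithmetic can fairly be called illustrative. Every rate and accuracy value is assumed, the documents say nothing about how well patients detect these signs, and the only named test is a t-test on means, with its outcome unspecified. The figures show sensitivity to error; they do not estimate it.

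**Conclusion.** The concern holds as a mismatch between label and measurement. By its own three-part definition, the plan describes no examination for the objective part, no listed question for the functional part and no grading step, so a WHO grade cannot be derived from the data described. This rests on the text alone.

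The bias has no known direction or size. Under the assumed 40% and 25%, the observed difference ranges from 21.8 points in favour of gum arabic, through 10.5 with equal error at 0.80/0.90, to 1.5 points against it. A 12-point difference can also arise from none. These values depend on the assumed accuracy and the even split. The conclusion that the direction is open depends only on the group being known and the outcome being self-reported.

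**What to change.** 1. Define and report the outcome as patient-reported oral mucositis, not as a WHO score, and limit the conclusion to that.
2. State whether anyone inspected the mouth at the hospital meetings, who did so, and whether it was recorded. If it was, report the inspected findings separately from the patients' answers, with the contact mode (telephone or hospital) marked. State also whether eating was asked about.
3. Add a sensitivity analysis that back-corrects each group's rate, p = (observed + Sp − 1) / (Se + Sp − 1), over a declared grid of equal and group-specific Se and Sp. Show which combinations would remove the group difference. As a check, 0.380 with 0.80/0.90 returns 0.28 / 0.70 = 0.40.

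These steps need no new data and only a little analysis time. The real cost is that the trial can no longer claim an objective or WHO-graded effect.

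Inspecting the mouth at return meetings, and measuring its agreement with patients' answers, can apply only to future use of this protocol because follow-up has ended. Even then it has limits. Opportunities would differ by regimen (5, 2 or 1 on-schedule meetings), and episodes that resolve between meetings would be missed.

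### Six calendar weeks of follow-up cover 6, 3 or 2 chemotherapy cycles depending on regimen, and no stratification or adjustment for regimen interval is described for the non-randomised comparison

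*Combined protocol and SAP*

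**What the plan says.** The combined protocol and SAP fixes follow-up by the calendar. Under *Assessment gum Arabic effect*, the data sheet is one "that will fill through six weeks of patient follow up", and the length is given as "Six weeks for each participant from starting therapy". Baseline information is that "which will record by researcher during the first day at first cycle of chemotherapy", so observation starts with cycle 1. Mucositis is assessed "by weekly telephone call for patient based on ready-scheduled appointments", the same for every regimen. The supply under *Dose, preparation and administration of gum arabic* matches: "The total number of sachets are 42 for a period of six weeks".

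The chemotherapy is not uniform. The researcher also meets patients "when the participant return to the next cycle of chemotherapy either weekly, bi-weekly or every three weeks, according to treatment regimen". *Inclusion criteria* sets no limit on regimen: "Patients whom well diagnosed with cancer in any stage were eligible for enrolment if chemotherapy is a part of the treatment plan".

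The objective is "to investigate the effect of Gum Arabic to prevent chemotherapy-induced oral mucositis in cancer patients". *Cessation of trial therapy* describes a three-week pause in recruitment to keep the study and control groups apart, with the aim of reducing confounding. No randomisation is described. *Statistical analysis* refers to 332 completers and says in general terms that the analysis suited the type of data. The only between-group test it names is the Student t-test.

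**The concern.** The outcome is mucositis caused by chemotherapy, so each cycle is a new occasion for it. A fixed calendar window gives weekly patients up to three times as many occasions as three-weekly patients. That is harmless if both groups contain the same mix of regimens, but nothing described in the plan secures this. Reading the pause as sequential recruitment, the two groups come from different calendar periods. A pause separates them in time; it does not balance their regimens.

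If the gum arabic group held fewer weekly patients, it could show less mucositis with no product effect. If it held more, a real effect could be hidden. The described analysis has no step that would detect or correct either.

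**Working it through.** **The plan's own figures.** The supply checks: 6 weeks × 7 days = 42 days = 42 sachets. The 332 cannot be reproduced, because no power, effect size, event rate or allocation is given.

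**Step 1: cycles in the window.** Inputs are days 1 to 42, cycle 1 on day 1, and intervals of 7, 14 and 21 days. Bi-weekly is taken as every two weeks, which its place between the other two suggests.

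- Weekly: days 1, 8, 15, 22, 29, 36 = 6 cycles.
- Two-weekly: days 1, 15, 29 = 3 cycles.
- Three-weekly: days 1, 22 = 2 cycles.

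A cycle on day 43 falls after the window; counting it would give 7, 4 and 3.

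**Step 2: six-week incidence.** The documents give no risk per cycle, so an independent risk *p*, equal in all regimens, is assumed. Incidence over *n* cycles is 1 − (1 − *p*)^*n*.

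| *p* per cycle | Weekly (*n* = 6) | Two-weekly (*n* = 3) | Three-weekly (*n* = 2) |
|---|---|---|---|
| 5% | 26.5% | 14.3% | 9.8% |
| 10% | 46.9% | 27.1% | 19.0% |
| 15% | 62.3% | 38.6% | 27.8% |

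**Step 3: effect of a different mix.** Let one group have a share *s* more weekly and *s* fewer three-weekly patients, with no product effect. The spurious difference is *s* × (weekly − three-weekly incidence).

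- *s* = 0.10: 0.10 × (0.265 − 0.098) = 0.017 at 5%; 0.10 × (0.623 − 0.278) = 0.035 at 15%.
- *s* = 0.20: about 0.033 at 5% and 0.069 at 15%.

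The range is 1.7 to 6.9 percentage points.

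**Step 4: chance of a false finding.** Assume mixes (weekly/two-weekly/three-weekly) of 40/30/30 and 20/30/50, and 166 per group (332 ÷ 2; the split is not stated). A normal-approximation test of two proportions at two-sided 5% gives:

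- 5% per cycle: 17.8% v 14.5%, difference 3.3 points; significant in that direction with probability about 13%.
- 10% per cycle: 32.6% v 27.0%, difference 5.6 points; about 20%.

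An unbiased test would give 2.5% in that direction.

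**Step 5: the other end of the range.** Suppose instead that risk per cycle grows with the interval, as 1 − (1 − *q*)^*w* for an interval of *w* weeks. Over 6/*w* cycles the chance of staying free is (1 − *q*)^6 for every regimen. With *q* = 5%, all three have an incidence of 1 − 0.95^6 = 26.5%, and a different mix creates no difference.

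**The case against.** Four objections deserve an answer.

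**Equal calendar follow-up is defensible.** It matches the six-week supply and gives every patient the same number of calls. This stands, and the window need not change. What is missing is a comparison that allows for what happens inside it.

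**The size is hypothetical.** Risk per cycle, its equality across regimens and the imbalance are all assumed, and the lower end is zero. The documents also do not name any mucositis within six weeks as the primary outcome. This stands as a limit on the figures. Means or durations would also be open to a regimen-mix effect, but that is not quantified here.

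**It is ordinary confounding in non-randomised groups.** Largely true. Regimen interval is nevertheless a named, easily obtained factor that changes the amount of exposure inside the window, so it merits its own adjustment.

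**The plan allows whatever analysis suits the data.** That wording leaves room for adjustment but describes none.

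A reader might go further and infer that mucositis delays later cycles, which lowers later risk unrecorded. The documents do not support this:

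- They never mention delayed, reduced or omitted cycles.
- The four questions to patients are given as a summary and the data sheet is not shown. The researcher meets patients at their cycles, and patient files were used. One can say only that recording of cycle delivery is not described.
- A delay that follows a first episode cannot change whether that patient ever had mucositis; it could affect only recurrence, duration or later weekly answers.
- A single one-week delay after cycle 1 removes a cycle from the window only for weekly patients (6 to 5). Two-weekly patients (days 1, 22, 36) keep 3, and three-weekly patients (days 1, 29) keep 2.
- A patient whose second cycle is withheld is not unexposed, since cycle 1 was given.

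**Conclusion.** The point holds as one of unequal exposure combined with an unadjusted, non-randomised comparison. The 6, 3 and 2 cycles follow directly from the plan, given on-schedule treatment and bi-weekly meaning every two weeks. The bias is possible, not demonstrated: the regimen mix by group is not reported.

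Its size is about 1.7 to 7 percentage points of six-week incidence under equal risk per cycle of 5% to 15% and a 10- to 20-point shift between three-weekly and weekly regimens. It is near zero if risk per cycle scales with the interval. The direction depends on which group has more weekly patients.

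A reader might also infer that cycle 1 should replace the six-week window as the main comparison. That does not follow. It would give unequal windows of 7, 14 or 21 days and discard five of a weekly patient's six cycles. In the equal-risk model it would cut weekly incidence from 62.3% to 15%, or from 26.5% to 5%.

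**What to change.** Recruitment and follow-up had ended by August 2016, so the remedy lies in analysis and file abstraction.

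1. Keep the six-week window. Take each patient's planned regimen interval from the patient files or data sheet, with the cycles actually received where available. Tabulate both by group.
2. Compare the groups within the weekly, two-weekly and three-weekly strata and combine: Mantel-Haenszel for occurrence, or a regression with regimen interval as a covariate for means or durations. Stratify on the planned interval, because cycles received may be affected by what happens after cycle 1. With no product effect and no other confounding, the expected difference in each stratum is zero, so the combined difference is zero whatever the risk per cycle.
3. Report a per-cycle result and a cycle-1 result, within the same strata, only as supportive.
4. Limit the conclusion to the first six weeks of chemotherapy.

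The cost is some file abstraction, one stratified table or model, and a small loss of precision. A stratum with patients from only one group adds nothing to the Mantel-Haenszel estimate. The fix removes the effect of regimen interval only; other differences in case mix, including the drugs given within an interval, remain.

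### The weekly interview, as summarised, asks about soreness, erythema and ulcers only after the patient says that oral mucositis occurred, so unrecognised disease can be recorded as absent

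*Combined protocol and SAP*

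**What the plan says.** The section on oral mucositis assessment names the WHO Oral Toxicity Scale and builds the assessment from components: "subjective – soreness as described by the patient, objective – presence of erythema and ulcerations", together with a functional item on eating.

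The section on assessing the gum arabic effect describes how the data are obtained. The first part of the data sheet is filled by "assessment patient regarding oral mucositis after chemotherapy by weekly telephone call for patient based on ready-scheduled appointments". In addition, "there is meeting with patients by researcher in chemotherapy rooms when the participant return to the next cycle of chemotherapy", which may be weekly, two-weekly or three-weekly depending on the regimen. At either kind of contact, "there will be specific questions directed by the researcher to be answered by the patient regarding oral mucositis". The questions are introduced as a summary. The first two are: "1. Does the oral mucositis was occurred during this week? 2. If Yes. Is there was soreness, erythema, ulcers in mouth of participant". The third asks for the days on which mucositis started and ended. The fourth, for the study group only, asks whether gum arabic is still used regularly. Follow-up is "Six weeks for each participant from starting therapy".

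The section on cessation of trial therapy says that recruitment and follow-up stopped by August 2016. The document is dated 15/11/2017.

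**The concern.** Under the WHO-based definition, the components come first and the presence of mucositis follows from them. The interview runs the other way: the patient supplies the diagnosis, and the components are asked about only if that diagnosis is affirmed. A negative first answer ends the enquiry for that week.

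The stated objective is prevention, so whether mucositis occurred is the natural main result, although no primary endpoint is formally defined. Three things are at stake:

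- Mild disease (soreness or redness alone) is what a patient is least likely to call oral mucositis, so it is the most exposed to loss.
- Start and end days are collected only for recognised episodes and can be shifted or shortened by late recognition.
- The interviewer knows the group, because question 4 is put only to the study group, and no blinding is described. Recognition, or the help given in understanding the term, could therefore differ between groups.

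This is a separate matter from the lack of an eating question in the summary. Here, items that are on the list are skipped.

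**Working it through.** **Text check.**

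| Step | Assessment definition | Interview as summarised |
|---|---|---|
| Starting point | Soreness, erythema, ulceration, eating | Patient's statement that oral mucositis occurred |
| Components | Asked or observed in order to establish mucositis | Asked only after a yes |
| After a negative answer | Not applicable | No further question or examination described |
| Contact modes | Not specified | Same questions "either by telephone call or when meeting participant in the hospital during the next chemotherapy cycle" |

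The hospital meetings do not repair this on the text. They use the same patient-answered questions, and no inspection of the mouth, plain-language definition or clinician confirmation is mentioned.

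**Illustration of size.** The plan gives no event rate, effect size or power, so there is no figure to reproduce.

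From the documents: 332 completers and a 0.05 significance level. Assumed: an equal split (332/2 = 166 per group), two-sided testing, the true incidences, the recognition rates, and no false positives.

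Recorded incidence = true incidence × s, where s is the probability that an affected patient is recognised at least once in the six weeks. With recorded rates p1 and p2, mean p̄ and difference d:

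- SE0 = √(2p̄(1−p̄)/166)
- SE1 = √((p1(1−p1)+p2(1−p2))/166)
- power = Φ((d − 1.96·SE0)/SE1)

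Example with s = 0.6: p1 = 0.40 × 0.6 = 0.24, p2 = 0.25 × 0.6 = 0.15, p̄ = 0.195, SE0 = 0.0435, SE1 = 0.0432. Then (0.09 − 1.96 × 0.0435)/0.0432 = 0.11, and power = 54.4%.

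*Equal recognition in both groups:*

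| True incidences | s = 1.0 | s = 0.8 | s = 0.6 |
|---|---|---|---|
| 40% vs 25% | 15 points, 83.4% | 12 points, 70.5% | 9 points, 54.4% |
| 50% vs 35% | 15 points, 79.2% | 12 points, 63.7% | 9 points, 46.8% |
| 30% vs 20% | 10 points, 55.8% | 8 points, 44.5% | 6 points, 33.3% |

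The absolute difference shrinks. The ratio does not under these assumptions: 25/40 = 15/24 = 0.625.

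*Unequal recognition, no true effect (40% in both groups):*

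| s in the two groups | Recorded | False difference | Chance of significance |
|---|---|---|---|
| 0.7 and 0.6 | 28% vs 24% | 4 points | 12.9% |
| 0.8 and 0.6 | 32% vs 24% | 8 points | 36.8% |
| 0.9 and 0.6 | 36% vs 24% | 12 points | 66.6% |

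The sign depends on which group recognises more.

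**Allowing for repeated contacts.** The gate acts at each weekly contact, not once per patient. If recognition per contact is r, and a patient is symptomatic at k contacts with independent answers, then s = 1 − (1 − r)^k. For k = 2:

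- r = 0.6 gives s = 1 − 0.4² = 0.84. The 40% vs 25% case is recorded as 33.6% vs 21.0% (12.6 points), power 73.3%.
- r = 0.8 gives s = 1 − 0.2² = 0.96, recorded as 38.4% vs 24.0% (14.4 points), power 81.1%.
- r = 0.8 in one group and 0.6 in the other, no true effect: recorded 38.4% vs 33.6%, a false 4.8 points, significant 14.7% of the time.

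A patient who does not know the term is likely to miss it every week, so answers will be correlated. The tables above correspond to k = 1 or to fully correlated answers; the k = 2 results show the independent case.

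**The case against.** The strongest reply is that the questions are presented as a summary and the data sheet itself is not shown. The sheet might prompt for symptoms regardless of the first answer, or the researcher might explain the term. This stands as a limit on certainty: the documents show that a symptomatic patient *can* be recorded as negative, not that any was. It does not remove the point, because the conditional step is itself part of the summary and nothing else in the text relaxes it.

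A second reply is that negatives may have been checked at the hospital meetings, or against the patient's personal file, which the statistical analysis section mentions as a source. Neither place says that a negative answer was verified. The supportable statement is that no verification is described, not that none took place.

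A third reply is that any size is invented and that several weekly contacts give several chances to be detected. Both parts stand. Losses at the single-contact level should not be read as losses per patient.

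A reader might also infer that the gate favours gum arabic. The documents do not support a direction. Patients given a preventive product could be more alert to the term or quicker to deny it.

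**Conclusion.** The point holds as a defect in the order of the questions. The summarised interview makes the component questions conditional on lay recognition of the diagnosis, contrary to the plan's own component-based definition, with no described check of a negative answer. Followed as written, it can under-record mucositis, chiefly mild disease, and can distort onset and end dates.

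The documents give neither recognition rates nor incidences, so they do not fix the size. Under the stated assumptions, equal recognition of 60% to 80% per patient cuts a 15-point difference to 9 to 12 points. Two independent symptomatic contacts at those rates limit the cut to 12.6 to 14.4 points. Unequal recognition could create a false difference in either direction, but this is a possibility and not a finding. It would go too far to conclude that cases were in fact missed, or that the trial's comparison is biased towards one group.

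**What to change.** **Data already collected.** Follow-up ended by August 2016, so reordering the questions cannot help these patients. Report the outcome as patient-recognised oral mucositis, not as WHO-scored incidence, and state possible under-ascertainment as a limitation. If the full data sheet contains component items asked regardless of the first answer, show them and use them instead. Any sensitivity calculation should cover a range of recognition rates, equal and unequal between groups, and allow for repeated contacts. The cost is wording and a short calculation.

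**The plan, and any further use of the form.** Remove the condition on the first answer. At every contact, ask every patient in both groups the same plain-language questions on soreness, redness, ulcers and ability to eat solids or liquids. The eating item is needed because the first three alone cannot give a WHO grade. Derive presence, grade and onset and end dates from these answers, and do not ask the patient for the diagnosis.

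The cost is a few more questions per call, with no extra visit or procedure. Recorded incidence will rise and will include some soreness from other causes. Redness and ulcers will still be self-reported on the telephone, so that limit remains and should be stated.
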